7.1.8 Survival follow-up

Subjects will enter the survival follow-up period once they complete the safety follow-up period. Subjects will then be contacted by telephone every 12 weeks to follow-up on their survival status. Any new antineoplastic medications that have been started since the last contact date will also be collected during these phone calls.

Following the final PFS analysis, which did not demonstrate a significant treatment benefit, the study will remain open for further follow-up to collect additional survival and safety data. Updated safety and descriptive analyses of overall survival will be performed.

For subjects who transferred to Post-Trial Access (PTA), no further survival follow-ups will be performed.

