10.5.1 Key secondary objectives

Part 1: Safety run-in and Part 2: Biomarker cohort

Not applicable.

Part 3: Double-blind, randomized, placebo-controlled part

The key secondary objective is to determine whether treatment with PDR001 in combination with dabrafenib and trametinib prolongs OS compared with dabrafenib and trametinib plus placebo. OS is defined as the time from date of randomization to date of death due to any cause. If a patient is not known to have died, then OS will be censored at the latest date the patient was known to be alive (on or before the cut-off date).

The following statistical hypotheses will be tested to address the key secondary efficacy objective for OS:

$$H_{02} : \theta_2 \geq 1 \text{ vs. } H_{12} : \theta_2 < 1$$

where θ_2 is the OS hazard ratio (PDR001 combined with dabrafenib and trametinib versus dabrafenib and trametinib plus placebo). The analysis to test these hypotheses and compare the two treatment groups will consist of a stratified log-rank test at an overall one-sided 2.5% level of significance. The stratification will be based on the randomization stratification factors, i.e., (LDH level: $< 1 \times \text{ULN}$ vs ≥ 1 to $< 2 \times \text{ULN}$ vs $\geq 2 \times \text{ULN}$; ECOG PS: 0 vs 1 vs 2).

OS analyses will be conducted as a part of a three-look group sequential design using a Lan-DeMets (O'Brien-Fleming) alpha spending function. Analyses will be based on the FAS population according to the randomized treatment group and strata assigned at randomization. The OS distribution will be estimated using the Kaplan-Meier method, and Kaplan-Meier curves, quartiles and associated 95% confidence intervals will be presented for each treatment group. The hazard ratio for OS will be calculated, along with its 95% confidence interval, using a stratified Cox model.

OS data will be presented at each analysis but will be formally tested hierarchically as follows:

If PFS is statistically significant at the interim PFS analysis:

Interim OS data will be tested at the time of the interim and final PFS analyses.

A final (inferential) analysis for OS is planned when approximately 245 deaths have occurred (or earlier if specifically requested by health authorities).

If PFS is not statistically significant at the interim PFS analysis:

Interim OS data will not be tested at the time of the interim PFS analysis.

If PFS is statistically significant at the final PFS analysis:

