- Date of discontinuation is the date of the end of treatment visit.
- Date of last contact is defined as the last date the patient was known to be alive. This corresponds to the latest date for either the visit date, lab sample date or tumor assessment date. If available, the last known date patient alive from the survival follow-up page is used. If no survival follow-up is available, the date of discontinuation is used as last contact date.
- Date of secondary anti-cancer therapy is defined as the start date of any additional (secondary) antineoplastic therapy or surgery.

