14.1.4.3 End of post-treatment follow-up (study phase completion)

End of post-treatment follow-up visit will be completed after discontinuation of study treatment and post-treatment evaluations but prior to collecting survival follow-up.

Patients may provide study phase completion information for one of the following reasons:

- Adverse event
- Lost to follow-up
- Physician decision
- Pregnancy
- Protocol deviation
- Technical problems
- Subject/guardian decision
- Death
- Progressive disease
- Study terminated by the sponsor

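### The last-contact bullet in Appendix 1 contradicts itself and the OS censoring rule in Section 10.5.1; programmed literally, it would lower each arm's OS curve

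*Protocol*

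**What the plan says.** The OS rule appears in three places in the protocol.

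- Section 10.5.1, for a subject not known to have died: "OS will be censored at the latest date the patient was known to be alive", limited to dates on or before the cut-off.
- Section 14.1.3.2.2 (Appendix 1, overall survival): censoring at the last date known alive. It mentions no EoT fallback.
- Section 14.1.3.2.7 (Appendix 1, end dates): "Date of last contact is defined as the last date the patient was known to be alive". It then adds: "This corresponds to the latest date for either the visit date, lab sample date or tumor assessment date". A survival-page date is used if there is one. The bullet closes with "If no survival follow-up is available, the date of discontinuation is used as last contact date". The bullet just above it says: "Date of discontinuation is the date of the end of treatment visit".

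On timing, Section 7.1.8 says: "Subjects will enter the survival follow-up period once they complete the safety follow-up period", with calls every 12 weeks after that. Section 7.1.6 runs safety follow-up to 150 days after the last PDR001/placebo dose, with contacts at 30, 60, 90, 120 and 150 days. Section 14.1.4.3 places the end of post-treatment follow-up after "post-treatment evaluations but prior to collecting survival follow-up". Section 7.1.7, for the period after the final PFS analysis, instead has subjects who stop treatment enter safety and OS follow-up at once.

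**The concern.** A subject can have known-alive dates after EoT and still have no survival page. Under Section 7.1.8 this is the ordinary state during safety follow-up. The start of the last-contact bullet and Section 10.5.1 then give the later date, while the bullet's last sentence gives the EoT visit.

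Deaths are not treated the same way. Section 14.1.3.2.7 takes dates of death during follow-up from the study evaluation completion page as well as from the survival page. A death in this window therefore counts on its true date with no survival page. Keeping the deaths while removing the survivors' time makes censoring depend on the outcome and pushes the Kaplan-Meier estimate down. OS is the key secondary endpoint and the only efficacy endpoint still collected, and in a descriptive report the curve, median and milestone rates are themselves the result.

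**Working it through.** **The plan's own OS figures.** Inputs from Section 10.9: control median 25 months, HR 1 for 5 months then 0.60, overall HR 0.693, one-sided 2.5%, 1:1 allocation, 80% power, 245 deaths.

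- Experimental median: 5 + (ln 2 − 5·ln 2/25)/(0.6·ln 2/25) = 5 + 0.8 × 25/0.6 = 38.3 months, as stated.
- Deaths by Freedman: (1.960 + 0.842)² × (1.693/0.307)² ≈ 239. By Schoenfeld: 4 × (1.960 + 0.842)²/(ln 0.693)² ≈ 234.
- Power at 245 deaths, single look: Φ(√245/2 × 0.3667 − 1.960) = Φ(0.910) = 81.9%. With three Lan-DeMets (O'Brien-Fleming) looks at four assumed sets of information fractions: 80.7% to 81.3%.

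The 245 deaths reproduce. None of these formulas uses the censoring rule, so they do not change with it.

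**One subject under both rules.** Suppose the EoT visit is 7 days after the last dose, the 120-day safety contact is made, and the cut-off falls on day 130. Under Section 7.1.8 there is no survival page yet. Section 10.5.1 censors at day 120. The fallback censors at day 7, a loss of 120 − 7 = 113 days. Had this subject died on day 125, the event would count on day 125.

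**Size if the fallback is programmed.** A single arm of 400,000 subjects was simulated with three states: on treatment, off treatment and dead. From the protocol: OS median 25 months, and cut-offs at about 25 months (projected final PFS analysis, Section 10.8) and 36 months (projected final OS analysis, Section 10.9). Assumed, because the protocol shown does not give them:

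- uniform accrual over 6, 12 or 18 months;
- exponential time to treatment stop, median 8, 11 or 14 months;
- on-treatment death hazard λ₁ = 0.005 per month;
- no survival page for 150 days (4.93 months) or 150 + 84 = 234 days (7.7 months) after treatment stops.

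With λd the hazard of stopping, the off-treatment death hazard λ₂ solves

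exp(−(λ₁+λd)·25) + λd/(λ₁+λd−λ₂) × [exp(−λ₂·25) − exp(−(λ₁+λd)·25)] = 0.5.

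For a median of 11 months, λd = 0.0630. With λ₂ = 0.060 the left side is 0.1826 + 7.86 × 0.0405 = 0.501.

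Subjects alive and off treatment for less than the lag at cut-off were censored at treatment stop (fallback) or at the cut-off (known alive). Selected results:

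| Cut-off | Accrual / treatment median / lag (months) | Subjects affected | 24-month OS, known alive → fallback | Median OS (months) |
|---|---|---|---|---|
| 25 | 6 / 8 / 4.93 | 6.4% | 0.520 → 0.511 | 25.0 → 24.5 |
| 25 | 12 / 11 / 4.93 | 8.9% | 0.518 → 0.505 | 24.8 → 24.2 |
| 25 | 12 / 11 / 7.7 | 14.2% | 0.519 → 0.490 | 25.0 → 23.6 |
| 25 | 18 / 8 / 7.7 | 20.4% | 0.521 → 0.486 | 25.0 → 23.4 |
| 36 | 6 / 8 / 4.93 | 2.4% | 0.521 → 0.521 | 25.0 → 25.0 |
| 36 | 12 / 11 / 7.7 | 6.6% | 0.518 → 0.516 | 24.9 → 24.7 |
| 36 | 18 / 11 / 7.7 | 8.5% | 0.520 → 0.513 | 25.0 → 24.6 |

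Over all 18 combinations per cut-off, 24-month OS falls by 0.9 to 3.5 points at 25 months and by 0 to 0.7 points at 36 months. The 12-month estimate moves by at most 1.2 points. The comparison somewhat overstates the loss, because it takes every survivor as known alive on the cut-off day itself.

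**The case against.** The strongest defence is that the trial's own OS rule is right. Section 10.5.1 is specific to this study, Section 14.1.3.2.2 agrees with it, and neither refers to EoT. Appendix 1 is a general sponsor guideline that leaves choices to the protocol. This stands to the extent that it shows what is intended. A reader might infer that OS in this trial is in fact censored at EoT and is biased. The documents do not support that, because the bias arises only if programming follows the one sentence.

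The defence does not make the sentence harmless. Section 10.5.1 gives the principle but not how the date is derived, and Section 14.1.3.2.7 presents its end dates as those used for time-to-event variables. The wording about guidance introduces Section 14.1.4. The wording about defaults belongs to Table 14-4, which covers PFS, time to progression and duration of response.

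Other limits also stand:

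- After the final PFS analysis, Section 7.1.7 starts OS follow-up at once and tumor results need no longer be recorded. On that text the gap may be short or absent, although Section 7.1.8 still says otherwise.
- The final PFS analysis, with cut-off 01-Jul-2020, is past. The remaining OS analyses are later and descriptive, so the 36-month rows are the more relevant ones.
- A reader might infer a biased treatment comparison. The calculation is for a single arm. A biased hazard ratio would need different patterns of stopping treatment between arms, and that is not shown.
- A reader might infer that subjects still on treatment get no censoring date. The first half of the bullet and Section 10.5.1 both give one.
- For subjects who move to post-trial access, follow-up under the protocol ends with the EoT visit, so the two rules agree.

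**Conclusion.** The point holds as an internal contradiction. The last sentence of the last-contact bullet conflicts with the start of that bullet, with Section 14.1.3.2.2 and with Section 10.5.1. Applied literally, it would lower each arm's OS curve. Under the assumptions listed, the fall in 24-month OS would be about 1 to 3.5 points at a 25-month cut-off and 0 to 0.7 points at 36 months. These sizes rest on assumed accrual, treatment duration, death hazards and survival-page lag, and on the fallback actually being used. No formal test is at stake, since OS testing closed when PFS was not significant. The sentence should be corrected, but nothing here shows that reported OS is wrong.

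**What to change.** Delete the last sentence of the date-of-last-contact bullet in Section 14.1.3.2.7. In its place, state that OS is censored at the latest date, on or before the cut-off, at which the subject was known to be alive from any collected source: visit, laboratory sample, tumor assessment, safety follow-up contact or survival follow-up. That matches Section 10.5.1. Reconcile Sections 7.1.7 and 7.1.8 so that the protocol states once when survival follow-up begins after treatment stops. The cost is two short text changes and, if the fallback has been programmed, a small change to one derived date. The dates needed are already collected.

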14.1.3.2.8 Sensitivity analyses

This section outlines the possible event and censoring dates for progression, as well as addresses the issues of missing tumor assessments during the study. For instance, if one or more assessment visits are missed prior to the progression event, to what date should the progression event be assigned? And should progression event be ignored if it occurred after a long period of a patient being lost to follow-up? It is important that the protocol and RAP specify the primary analysis in detail with respect to the definition of event and censoring dates and also include a description of one or more sensitivity analyses to be performed.

Based on definitions outlined in [Section 14.1.3.2.6](#), and using the draft FDA guideline on endpoints ([Clinical Trial Endpoints for the Approval of Cancer Drugs and Biologics April 2005](#)) as a reference, the following analyses can be considered:

[figure not shown]

Table 14-4 Options for event dates used in PFS, TTP, duration of response

[figure not shown]
Situation		Options for end-date (progression or censoring) ¹ (1) = default unless specified differently in the protocol or RAP	Outcome
A	No baseline assessment	(1) Date of randomization/start of treatment ³	Censored
B	Progression at or before next scheduled assessment	(1) Date of progression (2) Date of next scheduled assessment ²	Progressed Progressed
C1	Progression or death after exactly one missing assessment	(1) Date of progression (or death) (2) Date of next scheduled assessment ²	Progressed Progressed
C2	Progression or death after two or more missing assessments	(1) Date of last adequate assessment ² (2) Date of next scheduled assessment ² (3) Date of progression (or death)	Censored Progressed Progressed
D	No progression	(1) Date of last adequate assessment	Censored
E	Treatment discontinuation due to 'Disease progression' without documented progression, i.e. clinical progression based on investigator claim	(1) Ignore clinical progression and follow situations above (2) Date of discontinuation (visit date at which clinical progression was determined)	As per above situations Progressed
F	New anticancer therapy given	(1) Ignore the new anticancer therapy and follow situations above (ITT approach) (2) Date of last adequate assessment prior to new anticancer therapy (3) Date of secondary anti-cancer therapy (4) Date of secondary anti-cancer therapy	As per above situations Censored Censored Event
G	Deaths due to reason other than deterioration of 'Study indication'	(1) Date of last adequate assessment	Censored (only TTP and duration of response)

1. =Definitions can be found in Section 14.1.3.2.6.
 
2. =After the last adequate tumor assessment. "Date of next scheduled assessment" is defined in Section 14.1.3.2.6.
 
3. =The rare exception to this is if the patient dies no later than the time of the second scheduled assessment as defined in the protocol in which case this is a PFS event at the date of death.
			

The primary analysis and the sensitivity analyses must be specified in the protocol. Clearly define if and why options (1) are not used for situations C, E and (if applicable) F.

Situations C (C1 and C2): Progression or death after one or more missing assessments: The primary analysis is usually using options (1) for situations C1 and C2, i.e.

- (C1) taking the actual progression or death date, in the case of only one missing assessment.
- (C2) censoring at the date of the last adequate assessment, in the case of two or more consecutive missing assessments.

In the case of two or missing assessments (situation C2), option (3) may be considered jointly with option (1) in situation C1 as sensitivity analysis. A variant of this sensitivity analysis consists of backdating the date of event to the next scheduled assessment as proposed with option (2) in situations C1 and C2.

Situation E: Treatment discontinuation due to ‘Disease progression’ without documented progression: By default, option (1) is used for situation E as patients without documented PD should be followed for progression after discontinuation of treatment. However, option (2) may be used as sensitivity analysis. If progression is claimed based on clinical deterioration instead of tumor assessment by e.g., CT-scan, option (2) may be used for indications with high early progression rate or difficulties to assess the tumor due to clinical deterioration.

Situation F: New cancer therapy given: the handling of this situation must be specified in detail in the protocol. However, option (1) (ITT) is the recommended approach; events documented after the initiation of new cancer therapy will be considered for the primary analysis i.e. progressions and deaths documented after the initiation of new cancer therapy would be included as events. This will require continued follow-up for progression after the start of the new cancer therapy. In such cases, it is recommended that an additional sensitivity analysis be performed by censoring at last adequate assessment prior to initiation of new cancer therapy.

Option (2), i.e. censoring at last adequate assessment may be used as a sensitivity analysis. If a high censoring rate due to start of new cancer therapy is expected, a window of approximately 8 weeks performed after the start of new cancer therapy can be used to calculate the date of the event or censoring. This should be clearly specified in the SAP.

In some specific settings, local treatments (e.g., radiation/surgery) may not be considered as cancer therapies for assessment of event/censoring in PFS/TTP/DoR analysis. For example, palliative radiotherapy given in the trial for analgesic purposes or for lytic lesions at risk of fracture will not be considered as cancer therapy for the assessment of BOR and PFS analyses. The protocol should clearly state the local treatments which are not considered as antineoplastic therapies in the PFS/TTP/DoR analysis.

The protocol should state that tumor assessments will be performed every x weeks until radiological progression irrespective of initiation of new antineoplastic therapy. It is strongly recommended that a tumor assessment is performed before the patient is switched to a new cancer therapy.

Additional suggestions for sensitivity analyses

Other suggestions for additional sensitivity analyses may include analyses to check for potential bias in follow-up schedules for tumor assessments, e.g., by assigning the dates for censoring and events only at scheduled visit dates. The latter could be handled by replacing in [Table 14-4](#) the “Date of last adequate assessment” by the “Date of previous scheduled assessment (from baseline)”, with the following definition:

- **Date of previous scheduled assessment (from baseline)** is the date when a tumor assessment would have taken place, if the protocol assessment scheme was strictly followed from baseline, immediately before or on the date of the last adequate tumor assessment.

In addition, analyses could be repeated using the Investigators’ assessments of response rather than the calculated response. The need for these types of sensitivity analyses will depend on the individual requirements for the specific study and disease area and have to be specified in the protocol or RAP documentation.

14.1.4 Data handling and programming rules

The following section should be used as guidance for development of the protocol, data handling procedures or programming requirements (e.g., on incomplete dates).

14.1.4.1 Study/project specific decisions

For each study (or project) various issues need to be addressed and specified in the protocol or RAP documentation. Any deviations from protocol must be discussed and defined at the latest in the RAP documentation.

The proposed primary analysis and potential sensitivity analyses should be discussed and agreed with the health authorities and documented in the protocol (or at the latest in the RAP documentation before database lock).

14.1.4.2 End of treatment phase completion

Patients **may** voluntarily withdraw from the study treatment or may be taken off the study treatment at the discretion of the investigator at any time. For patients who are lost to follow-up, the investigator or designee should show "due diligence" by documenting in the source documents steps taken to contact the patient, e.g., dates of telephone calls, registered letters, etc.

The end of treatment visit and its associated assessments should occur within 7 days of the last study treatment.

Patients may discontinue study treatment for any of the following reasons:

[figure not shown]
- Adverse event(s)
- Lost to follow-up
- Physician decision
- Pregnancy
- Protocol deviation
- Technical problems
- Subject/guardian decision
- Progressive disease
- Study terminated by the sponsor
- Non-compliant with study treatment
- No longer requires treatment
- Treatment duration completed as per protocol (optional, to be used if only a fixed number of cycles is given)

Death is a reason which “**must**” lead to discontinuation of patient from trial.

14.1.4.3 End of post-treatment follow-up (study phase completion)

End of post-treatment follow-up visit will be completed after discontinuation of study treatment and post-treatment evaluations but prior to collecting survival follow-up.

Patients may provide study phase completion information for one of the following reasons:

- Adverse event
- Lost to follow-up
- Physician decision
- Pregnancy
- Protocol deviation
- Technical problems
- Subject/guardian decision
- Death
- Progressive disease
- Study terminated by the sponsor

14.1.4.4 Medical validation of programmed overall lesion response

In order to be as objective as possible the RECIST programmed calculated response assessment is very strict regarding measurement methods (i.e. any assessment with more or less sensitive method than the one used to assess the lesion at baseline is considered UNK) and not available evaluations (i.e. if any target or non-target lesion was not evaluated the whole overall lesion response is UNK unless remaining lesions qualified for PD). This contrasts with the slightly more flexible guidance given to local investigators (and to the central reviewers) to use expert judgment in determining response in these type of situations, and therefore as a consequence discrepancies between the different sources of response assessment often arise. To ensure the quality of response assessments from the local site and/or the central reviewer, the responses may be re-evaluated by clinicians (based on local investigator data recorded in eCRF or based on central reviewer data entered in the database) at Novartis or external experts. In addition, data review reports will be available to identify assessments for which the investigators' or central reader's opinion does not match the programmed calculated response based on RECIST criteria. This may be queried for clarification. However, the investigator or central reader's response assessment will never be overruled.

If Novartis elect to invalidate an overall lesion response as evaluated by the investigator or central reader upon internal or external review of the data, the calculated overall lesion response at that specific assessment is to be kept in a dataset. This must be clearly documented in the RAP documentation and agreed before database lock. This dataset should be created and stored as part of the 'raw' data.

[figure not shown]
Any discontinuation due to 'Disease progression' without documentation of progression by RECIST criteria should be carefully reviewed. Only patients with documented deterioration of symptoms indicative of progression of disease should have this reason for discontinuation of treatment or study evaluation.

